Appendix III

Interpretation of Hepatitis B Serologic Test Results

Interpretation of Hepatitis B Serologic Test Results

HBsAg	negative	Susceptible
anti-HBc	negative	
anti-HBs	negative	
HBsAg	negative	Immune due to natural infection
anti-HBc	positive	
anti-HBs	positive	
HBsAg	negative	Immune due to hepatitis B vaccination
anti-HBc	negative	
anti-HBs	positive	
HBsAg	positive	Acutely/Chronically infected
anti-HBc	positive	
anti-HBs	negative	
HBsAg	negative	Interpretation unclear; four possibilities: 1. Resolved infection (most common) 2. False-positive anti-HBc, thus susceptible 3. "Low level" chronic infection 4. Resolving acute infection
anti-HBc	positive	
anti-HBs	negative

Panel 4	CCI [REDACTED]	50
Panel 5	CCI [REDACTED]	50
Panel 6	Visit Windows - Laboratory Tests, Vital Signs, Body Weight, ECG and C-SSRS.	52
Table 1	Trial Procedures and Assessments.....	61
Table 2	PCS Criteria for Clinical Safety Laboratory Tests	74
Table 3	PCS Criteria for Vital Signs, Weight/BMI, and Waist Circumference	75
Table 4	PCS Criteria for ECG Parameters.....	76
Table 5	CCI [REDACTED]	78

List of Abbreviations and Definitions of Terms

ADA	anti-drug antibody
ANCOVA	analysis of covariance
APRS	all-patients-randomized set
APTS	all-patients-treated set
CCI	[REDACTED]
CCI	[REDACTED]
BMI	body mass index
CCI	[REDACTED]
CGRP	calcitonin gene-related peptide
CI	confidence interval
CM	chronic migraine
COA	clinical outcome assessment
C-SSRS	columbia suicide severity rating scale
DILI	drug-induced liver injury
DMC	Data Monitoring Committee
ECG	electrocardiogram
eCRF	electronic case report form
eDiary	electronic diary
EM	episodic migraine
CCI	[REDACTED]
FAS	full-analysis set
FAS-LT	full analysis set long term
HD	Headache day(s)
CCI	[REDACTED]
HLGT	high level group term
HLT	high level term
CCI	[REDACTED]
ICE	intercurrent event
IMP	investigational medicinal product
CCI	[REDACTED]
CCI	[REDACTED]
MedDRA	Medical Dictionary for Regulatory Activities
MD	migraine day(s)
MHDs	monthly headache days
ML	maximum likelihood
MMDs	monthly migraine days
MMRM	mixed model for repeated measurements
MOH	medication overuse headache

CCI	
NAb	neutralizing antibody
PACAP	pituitary adenylate cyclase-activating polypeptide
PCS	potentially clinically significant
PD	Pharmacodynamic(s)
PK	pharmacokinetic(s)
CCI	
CCI	
QT	specific ECG interval describing ventricular depolarization/repolarization
QTc	heart rate-corrected QT interval
REML	restricted maximum likelihood
SAE	serious adverse event
SAP	Statistical Analysis Plan
SAS [®]	statistical software package from the SAS [®] Institute
SMQ	standardised MedDRA Query
SOC	system organ class
TEAE	treatment-emergent adverse event
VAS	visual analogue scale

Objectives	Endpoints
Primary Objective (continued)	
■ [REDACTED]■ [REDACTED]

CCI [REDACTED]• CCI [REDACTED]	
CCI [REDACTED][REDACTED][REDACTED][REDACTED][REDACTED][REDACTED][REDACTED][REDACTED][REDACTED][REDACTED][REDACTED]

Objectives	Endpoints

Safety Objective
 
 To evaluate the safety and tolerability of Lu AG09222 	
Safety Endpoints
 
 - Adverse events - Absolute values and changes from baseline in clinical safety laboratory test values, vital signs (blood pressure, pulse rate, respiratory rate, and body temperature), weight, and ECGs - Potentially clinically significant clinical safety laboratory test values, vital signs, weight changes, and ECG parameter values - Development of specific ADAs including NABs - C-SSRS score

2 Trial Design

This is an interventional, multi-national, multi-site, randomized, double-blind, parallel-group, placebo-controlled Phase IIa trial designed to demonstrate proof-of-concept, that is, to investigate whether the inhibitory action of Lu AG09222 on the PACAP pathway can be an effective mechanism for migraine prevention.

The target population for this trial is defined as participants diagnosed with migraine as outlined in the International Classification of Headache Disorders Third Edition (ICHD-3) guidelines, with documented evidence of migraine occurring on CCI per month prior to screening, as confirmed via prospectively collected information in the electronic diary (eDiary) during the screening period and with documented evidence of failure of 2 to 4 different preventive migraine medications in the past 10 years. Participants with a concurrent diagnosis of medication overuse headache (MOH) are allowed in the trial.

The aim is that approximately 30% of the randomized participants will have episodic migraine (EM; participants with headache occurring on <15 days). This will be ensured through a cap on the number of randomized EM participants. CCI

A total of 230 participants, recruited from specialist settings, will be randomly allocated via a randomization system to one of three treatment groups: Lu AG09222 CCI Lu AG09222 CCI, or placebo, in a ratio of 2:1:2.

Randomization will be stratified by region (North America versus Europe) and CCI

The total trial duration from the Screening Visit to the Safety Follow-up Visit is approximately 16 weeks and includes a Screening Period (28 to 30 days) and Safety Follow-up period is 12 weeks (includes the 4 weeks Treatment Period).

Participants will receive the investigational medicinal product (IMP) in the form of a single-dose administration at the Baseline Visit with either Lu AG09222 or placebo by intravenous (IV) infusion over 30 minutes (+15 minutes).

Participants will complete a daily headache eDiary from the Screening Visit until the Safety Follow-up Visit or Efficacy Follow-up/Withdrawal Visit.

During the Baseline Visit, assessments of safety will be performed before and after the infusion. At this visit, adverse event details will be collected as well as safety laboratory test results, ECG results, weight, vital signs findings, and blood samples CCI [REDACTED] ADAs including NABs, CCI [REDACTED]

Participants must complete the eDiary recording of headaches that ended prior to infusion (i.e., for headaches not yet recorded in the eDiary).

[figure not shown]
Participants who complete the trial will attend a Safety Follow-up Visit at 8 weeks (Week 12) after the Primary Outcome Visit.

Participants who withdraw prior to the Primary Outcome Visit (Week 4), except for those who withdraw their consent, will have a Withdrawal Visit as soon as possible, an Efficacy Follow-up (Phone Contact) Visit at Week 4, and a further Safety Follow-up Visit at 12 weeks after administration of the IMP (the Baseline Visit). If the Withdrawal Visit takes place at Week 4, an Efficacy Follow-up (Phone Contact) Visit at Week 4 is not required.

CCI [REDACTED]

The trial design is presented in [Panel 2](#) (including the trial periods) and the scheduled trial procedures and assessments are summarized in [Appendix II](#).

Panel 2 Trial Design

IMP = investigational medicinal product.

The trial consists of a screening period (28 to 30 days), a treatment period (4 weeks), and a safety follow-up period (12 weeks after IMP administration). IMP (Lu AG09222 CCI, Lu AG09222 CCI, or placebo) will be administered by intravenous infusion at the Baseline Visit. At Week 4, participants will complete the Primary Outcome Visit and will return to the clinic 8 weeks later (12 weeks after IMP administration) for a Safety Follow-up Visit.

3 COVID-19

For this trial, all participants are considered to have been enrolled after the beginning of the COVID-19 outbreak.

The following information is collected with regards to COVID-19:

- Whether a visit was done remotely due to COVID-19 including which assessments were/were not performed
- If a visit was not done, whether it was not done due to COVID-19
- Whether participants withdrew due to the COVID-19 situation
- Whether participants got diagnosed with COVID-19

The information collected with respect to COVID-19 will be presented in data listings.

COVID-19 vaccinations are allowed provided the vaccinations have been completed for at least 14 days prior to the Screening Visit. Vaccinations during the trial are allowed providing the vaccination is received at least 3 days after the IMP administration. The vaccinations, including brand names, if used during the trial, will be reported as concomitant medications.

4 Definitions

4.1 Definition of Baseline

For the endpoints based on daily recordings in the eDiary that are summarized in a monthly measure, the baseline value will be based upon the data recorded daily in the headache eDiary during the first 28 days following the Screening Visit.

For the endpoints based on daily recordings in the eDiary that are summarized in a weekly measure is derived as the average of the weekly values of the 28-day screening period.

For all other endpoints, the baseline assessment will be the latest available valid measurement taken prior to the administration of IMP.

4.2 Definition of Periods

The trial consists of the following periods:

- Screening Period (28-30 days): Starts at the Screening Visit (Visit 1) and continues up to start of Visit 2 IMP infusion (Week 0).
- Treatment Period (4 weeks): Starts at start of Visit 2 IMP (Week 0) infusion and continues up to and including Visit 4 (Week 4).
- Safety Follow-up Period (12 weeks): Starts at start of Visit 2 IMP (Week 0) infusion and continues up to and including the Safety Follow-up visit (Week 12).

4.3 Definition of Withdrawal

Participants who have received IMP infusion at Visit 2 and have withdrawn from the trial prior to the Primary Outcome Visit (Week 4), will be described as withdrawn from trial. The complementary group will be described as completed the trial.

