8.9 Withdrawal Visit

Patients who withdraw from the study prior to the Primary Outcome Visit (Week 4) will have a Withdrawal Visit, if possible, which can be conducted as a visit to the site or a home visit with or without a televisit. The visit must be scheduled as soon as possible after withdrawal.

At the Withdrawal Visit, a compliance check of the eDiary will be conducted. The eDiary assessments should continue on a daily basis until Week 4. Thus, if the patient withdraws between Week 3 and Week 4, then the Withdrawal Visit should be scheduled at Week 4 to align with the eDiary closeout. If the Withdrawal Visit takes place during the treatment period and prior to Week 3, then the eDiary assessments should continue on a daily basis until Week 4 and the patient will be contacted via telephone for an Efficacy Follow-up Visit (phone contact) at Week 4 for the eDiary closeout (see section 8.10). Details will be provided in a separate *eDiary and PRO training material*. See section 9.2.1.2 for further details on the eDiary.

PROs which are scheduled in alignment with the Withdrawal Visit can be completed on the day or within 3 days prior to the scheduled visit date. CCI

It is preferable that the same order of assessments is used per patient and if the scheduled time of the day for the assessments is as consistent as possible across all the study visits. It is preferred to take the CCI in the morning, if possible. This may put the CCI out of the order in relation to the other assessments when performed in the morning. See section 9.2.1 for further details on PROs. CCI must be administered by the authorized rater after the PROs are completed.

Blood sampling will be taken for CCI and ADA (including NAb) quantification, and optional CCI. Relevant assessments for safety will be conducted including blood and urine sampling for clinical safety laboratory tests and C-SSRS. C-SSRS must be administered by the authorized rater after the PROs are completed. Adverse events, concomitant medication (prescription and non-prescription), and non-pharmacological interventions will be collected.

No new information will be collected from patients who withdraw from the study, except information collected in relation to the scheduled Withdrawal Visit or needed for the follow-up of adverse events (section 10.5).

The reason for withdrawal must be recorded in the eCRF.

For a patient who withdraws consent:

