- If the patient withdraws consent during a visit and then agrees to it being the final visit, the investigator will complete the visit as a Withdrawal Visit and all the data collected up to and including that visit will be used.
- If the patient withdraws consent during a telephone conversation, the investigator will ask the patient if he or she will attend a Withdrawal Visit. If the patient:
 - Agrees to attend a Withdrawal Visit, all the data collected up to and including that visit will be used
 - Refuses to attend a Withdrawal Visit, the investigator should attempt to follow the patient's safety and future treatment; any information collected will only be recorded in the patient's medical records
- If the patient explicitly requests that the patient's data collected from the time of withdrawal of consent onwards not be used, this will be respected.

The withdrawal visit does not apply if a patient withdraws during the safety follow-up period (for whatever reason). Then the investigator should attempt to follow the patient's safety and future treatment; any information collected will only be recorded in the patient's medical records.

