16.4 Patient Disposition

Patient disposition will be summarized by treatment group and include the number of patients in the APTS who completed or withdrew prior to Week 4, as well as the number of patients in each analysis set described in section 16.2.

The number of patients who completed or withdrew from the study will also be summarized.

The number of patients who withdrew prior to Week 4 will be summarized by treatment group and primary reason for withdrawal as well as by treatment group and all reasons for withdrawal.

The number of patients who did not complete the study will be summarized by treatment group and the reason for withdrawal from the study.

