7.1 Summary of Participant Disposition

Participant disposition will be summarized by treatment group and include the number of participants in each analysis set defined in section 5, and the number of participants in the APTS who completed or withdrew from trial.

If any visits are changed from clinic to remote, a table will be provided presenting by type of visit (on clinic or remote) and treatment group.

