7.2 Withdrawals

The number of participants who withdraw from the trial will be summarized by treatment group. The primary reason for withdrawal will be presented, as well as all reasons for withdrawal.

Participants who withdrew from the trial will be listed and the listing will include the number of days in the trial until withdrawal from the trial, the number of days on IMP, the primary reason for withdrawal, all reasons for withdrawal, and a flag if the drug code was broken.

Kaplan-Meier failure plots of time to withdrawal will be presented by treatment group. The time will be calculated from the date of IMP to the date of withdrawal in the Treatment Period. Participants who complete the Treatment Period will be regarded as censored at the End of Week 4 visit (Visit 4).

All tables, graphs, and listings will be based on the APTS.

8 Demographics and Baseline Characteristics

Demographics (sex, age, age group, race and region); baseline characteristics (height, weight, and BMI); baseline disease characteristics; and baseline efficacy variables will be summarized by treatment group.

All the demographics and baseline characteristics data described below will be summarized based on the APTS.

The baseline disease characteristics comprise of:

- age and age group (≤ 21 years, > 21 years) at first diagnosis of migraine
- time since first migraine ICHD-3 diagnosis (years)
- time since first migraine diagnosis group (≤ 15 years, > 15 years)
- current type of migraine (CM or EM)
- time since current migraine ICHD-3 diagnosis (years)
- CCI

o CCI [REDACTED]

- has an MOH diagnosis (yes/no)
- for women: whether migraines started before or after menarche
- for men: whether migraines started before or after puberty
- whether the start of migraine was related to any event

The eDiary reported baseline headache and migraine characteristics (data collected on daily basis during the screening period) that will be summarized are:

- number of baseline MMDs
- number of baseline MHDs

CCI [REDACTED]

CCI [REDACTED]

CCI [REDACTED]

Concurrent as well as relevant past medical, neurological, and psychiatric disorders will be coded using the MedDRA, Version 25.0 (or later) and summarized by treatment group.

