13.1.8 Presentation of Adverse Events Leading to Withdrawal

All the adverse events leading to withdrawal will be listed for the APRS.

TEAEs leading to withdrawal will be summarized by:

- SOC and preferred term
- preferred term

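### SAP 4.3 counts everyone treated who passes Week 4 as a trial completer, so Weeks 5–12 withdrawals vanish from the disposition summaries that Protocol 16.4 asks for

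*SAP*

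**What the plan says.** SAP 4.3 sets one cut-off. Participants who received the infusion and withdrew before the Primary Outcome Visit at Week 4 are described as withdrawn from the trial. For all others: "The complementary group will be described as completed the trial". There is no Week 12 condition.

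The disposition outputs use these terms. SAP 7.1 reports "the number of participants in the APTS who completed or withdrew from trial". SAP 7.2 summarises and lists those who withdrew from the trial, with reasons, and its Kaplan-Meier plot censors at Visit 4 those who complete the Treatment Period.

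Other sections place the end of the trial later:

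- SAP 2 gives a total duration of about 16 weeks, ending at the Safety Follow-up Visit, and states: "Participants who complete the trial will attend a Safety Follow-up Visit at 8 weeks (Week 12) after the Primary Outcome Visit".
- SAP 4.2 includes a period that runs to Week 12.
- Protocol 8.11 ends the study for a patient at the last protocol-specified contact.
- Protocol 8.9 provides for patients who withdraw during safety follow-up; no Withdrawal Visit applies to them.

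Protocol 16.4 asks for completion or withdrawal before Week 4 and, in addition, for completion of or withdrawal from the study. On the second it says: "The number of patients who did not complete the study will be summarized by treatment group and the reason for withdrawal from the study".

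**The concern.** The SAP gives the study-level label to a Week 4 status. Under its rule a participant who is lost to follow-up, withdraws consent or is withdrawn by the investigator in Week 6 has completed the trial. That participant appears in no withdrawal table or listing defined by SAP 4.3.

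A code break shows the effect. Protocol 6.6 requires immediate withdrawal when the code is broken, and the SAP 7.2 withdrawal listing carries a flag for it. A break in Week 6 would not reach that listing.

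Weeks 5–12 are 8 of the 12 post-dose weeks. They hold most of the safety follow-up, and the protocol assesses maintenance of effect there in the FAS-LT. A reader needs to know who left in that time, from which arm and why. If anyone does leave, the disposition table overstates completion and a summary specified in the protocol is absent.

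**Working it through.** **Comparing the passages.** Take a treated participant who withdraws in Week 6.

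| Source | Status of this participant |
|---|---|
| SAP 4.3, used in SAP 7.1 and 7.2 | Completed the trial; no reason tabulated |
| SAP 2 and 4.2 | Left before the trial's last visit and period ended |
| Protocol 8.9 | Withdrew during safety follow-up |
| Protocol 16.4, Week 4 summary | Completed to Week 4 |
| Protocol 16.4, study summary | Did not complete the study; reason to be tabulated |

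SAP 4.3 agrees with the Week 4 line of Protocol 16.4 but carries the name of the study line. No readable SAP section supplies the study line.

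**Can other outputs fill the gap?** The denominators in SAP 13.2 count non-missing values at each visit, so n would fall, but without status or reason. SAP 13.1.8 lists all adverse events leading to withdrawal for the APRS and adds: "TEAEs leading to withdrawal will be summarized by" SOC and preferred term. These may show late withdrawals due to adverse events, although the SAP does not say whether the 4.3 cut-off applies to the summaries. Neither output gives completion status or reasons other than adverse events.

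**Size.** The plan states no completer count to reproduce. Its total does reproduce: 43/0.95 = 45.3, rounded up to 46, and 2:1:2 gives 92 + 46 + 92 = 230. The documents give no Weeks 5–12 withdrawal rate, so the following is illustrative. Assume N = 230 all treated and a constant withdrawal rate r per 4 weeks:

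- completers under SAP 4.3 = N(1 − r)
- completers at Week 12 = N(1 − r)³
- mislabelled = the difference

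| Assumption | SAP 4.3 completers | Week 12 completers | Mislabelled |
|---|---|---|---|
| r = 0 | 230 (100%) | 230 (100%) | 0 |
| 5% over 12 weeks, r = 1 − 0.95^(1/3) = 0.0170 | 226.1 (98.3%) | 218.5 (95.0%) | 7.6 |
| r = 0.02 | 225.4 (98.0%) | 216.5 (94.1%) | 8.9 |
| r = 0.05 | 218.5 (95.0%) | 197.2 (85.7%) | 21.3 |

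With no loss before Week 4 and then 5% per 4 weeks, the number mislabelled is 230 × (1 − 0.95²) = 22.4.

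A second approach fixes 5% (12 participants) withdrawn before Week 4. SAP 4.3 then always reports 218 (94.8%) as completed. If a further 0, 2.5, 5 or 10% of the 230 leave in Weeks 5–12, the true counts are 218, 212, 206 or 195 (94.8, 92.2, 89.6 or 84.8%). The number mislabelled is 0, 6, 12 or 23.

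**The case against.** The strongest reply is that this is a naming matter. SAP 4.3 states its definition openly, and under that definition the count is right. Several supporting points deserve weight:

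- The SAP 2 sentence on completers is followed directly by one on participants who withdraw before Week 4. Read alone, it could mean that Week 4 completers go on to attend Week 12. The 16-week duration, the periods in SAP 4.2 and Protocol 8.11 tell against that reading, and the conflict with Protocol 16.4 does not depend on it.
- SAP 21, on changes from the protocol, is redacted, so a declared change cannot be excluded. A declaration would explain the departure from Protocol 16.4, but the label would still not fit SAP 2 and 4.2.
- The SAP 13.1.8 listing covers all adverse events leading to withdrawal and is not limited to Week 4. This stands, and it narrows the gap to completion status and non-adverse-event reasons.
- The line in Protocol 8.9 that sends information only to medical records may concern follow-up after withdrawal, not the withdrawal itself. That is a fair reading, so eCRF capture is a point to check and not an established gap.
- The 5% is a sample-size allowance, and spreading it over 12 weeks is an assumption. This stands; the true number is unknown and may be zero.

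None of these supplies the study-level summary or makes a Week 6 withdrawal a completion of the trial.

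**Conclusion.** The concern holds. As written, the SAP reports any Weeks 5–12 withdrawal as a trial completion, and its readable text omits the study-level disposition summary, with reasons, that Protocol 16.4 specifies.

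The number misclassified equals the number of late withdrawals, which the documents do not allow anyone to estimate. The illustrations run from 0 to the low twenties out of 230, assuming all are treated and the stated rates apply. The text finding needs none of these assumptions.

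The consequence is confined to disposition reporting and to the interpretation of safety and maintenance-of-effect data after Week 4. The primary Weeks 1–4 comparison, its type I error and the sample size do not change. This should be corrected, but it does not threaten the main result.

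**What to change.** 1. In SAP 4.3, rename the existing categories as completed or withdrew from the Treatment Period (Week 4), matching the term SAP 7.2 already uses for that milestone.
2. Add a second pair, completed or withdrew from the trial, defined by the Week 12 Safety Follow-up Visit. Summarise it by treatment group with reasons, as Protocol 16.4 states, and extend the SAP 7.2 withdrawal listing to match.
3. State in SAP 13.1.8 which definition governs the adverse-event withdrawal tables.
4. Confirm that the eCRF records status and reason for withdrawals after Week 4. Protocol 8.9 says "The reason for withdrawal must be recorded in the eCRF", but this instruction sits in the Withdrawal Visit section, and that visit does not apply to late withdrawals.

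The cost is SAP wording and one more disposition table. Step 4 comes first: the table can give reasons only if they were collected.
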